Aim 1. Test competing hypotheses regarding the effects of family history of alcoholism on alcohol analgesia. A substantial body of evidence suggests that individuals with FH of alcoholism (FH+) have differential subjective responses to acute alcohol administration compared to FH-, including greater pain reduction (Stewart et al., 1995; Ralevski et al., 2010). **Hypothesis (H)1.** We hypothesize that alcohol administration will be associated with greater reduction in pain sensitivity in FH+ than FH- individuals. Based on our pilot data, we also predict **H2.** FH+ individuals will report lower subjective ratings of relief from pain after consuming alcohol. Confirmation would suggest FH+ individuals may self-administer greater quantities of alcohol to achieve pain relief, consistent with the Low Level of Response (LLR) model (Morean and Corbin, 2010). Disconfirmation would suggest the negative reinforcing effects of alcohol

may be especially pronounced in FH+ (i.e., sensitization). Previous studies suggest typical alcohol use, motivations to drink, and personality factors may influence alcohol analgesia, suggesting a critical role of conditioning and expectancies (Brown et al., 1977; Cutter et al., 1979; Ralevski et al., 2010). On the basis of our pilot data, we predict **H3**. FH+ individuals will have stronger positive expectancies regarding alcohol analgesia, which will predict analgesic response to alcohol administration. Results also suggest **H4**. a conditioning effect such that individuals who endorse greater and more frequent alcohol consumption will experience a greater analgesic effect of alcohol.

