fMRI Heat Pain Protocol. Three task-based fMRI runs will be conducted subsequent to resting-state scanning using a noxious thermal stimulation protocol. This protocol has been previously used in an NIH-funded study in which [name] is a co-investigator (R01AT006334). For this task, a long MR-compatible thermal probe attached to a Medoc Q-Sense fMRI compatible thermal stimulator will be used to deliver noxious thermal stimuli. Blocks of thermal stimuli will be delivered to the glabrous skin of the foot at the individually calibrated temperature determined during the screening visit. Following each thermal stimulation block, participants will rate levels of pain intensity and perceived relief from alcohol. Each block will be preceded and/or followed by a 30-second rest blocks. An electronic VAS will be presented following each thermal stimulation block for the purposes of rating pain intensity (anchored from "No pain at all" to "Most intense pain imaginable"). After each run, participants will rate their perceived degree of relief from pain as a result of consuming their beverage using an electronic

VAS anchored from “No relief at all” to “Most profound relief imaginable”. Runs will last for approximately 6 minutes, and will take place consecutively.

Power Analysis. Power analysis and recruitment goals are based on results of our pilot study (see attached grant document for a detailed description of results). Power analyses were performed assuming two-tailed hypothesis tests. Effect sizes are reported as Cohen’s d, r, or f^2 (Cohen, 1988).

Our pilot data suggested statistically large increases in pain threshold temperature ($d = 1.16$) associated with BrACs $\sim .052$ g/dL. Effects on pain tolerance temperature and intensity ratings were smaller ($d = .28$); however, our targeted sample of 110 completers will provide $\sim 80\%$ power these effects, and $> 99\%$ power to detect effects of alcohol on pain threshold.

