FH of alcoholism was associated with greater expectancy of pain relief from alcohol intake in our pilot work ($d = 1.12$), as well as lower ratings of pain relief ($d = .54$). Effects of sex on these measures were large ($d > .88$). Sex also appeared to be a potent moderator of alcohol analgesia ($d > .90$), with women showing stronger analgesic effects. Our sample will provide $> 80\%$ power to detect these effects. FH was associated with smaller effects on alcohol-related reductions in pain intensity ($d = .42$), as well as pain threshold and tolerance ($d < .26$), resulting in $\sim 54\%$ power to detect interactive effects of FH and dose on these measures.

Across participants, preliminary data suggested small-to-moderate correlations between expectancy of pain relief from alcohol, ratings of pain relief, and typical daily drinking and reductions in pain sensitivity ($.26 < r < .44$). We anticipate $\sim 80\text{-}99\%$ power to detect these effects. However, our data also suggested that sex and FH may moderate these relationships. The interaction of sex and expectancy of pain relief strongly predicted increases in pain threshold and tolerance associated with alcohol intake ($f^2 > 1.11$). A similar effect was detected for the interaction of FH and expectancy of pain relief ($f^2 > .81$). A weaker interaction of FH and ratings of relief on QST measures was also detected ($f^2 > .37$). Likewise, interactions of sex with typical daily drinking and ratings of relief showed some relation to QST changes ($f^2 < .21$). We anticipate $> 94\%$ power to detect each of these interactions. There was little evidence of Sex or FH interactions with typical drinking on alcohol analgesia ($f^2 < .04$). Effect sizes of FH X Sex X expectancy/relief/typical drinking interactions could not be assessed given our limited sample; however, we anticipate sensitivity to detect an interactive $f^2 > .14$ with 80% power given our recruitment target.

Data Analysis Strategy. Data will be analyzed using SPSS 24 (IBM Corp., Armonk, NY).

Aim 1. Test competing hypotheses regarding the effects of family history of alcoholism on alcohol analgesia. To assess hypotheses related to Aim 1, FH status will be included as an independent variable in repeated measures general linear models analyses (rmGLM; SPSS GLM procedure; repeated: dose), with pain threshold/tolerance and intensity ratings, associated relief ratings, expectancy of pain

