relief from alcohol, and SEAS measures (i.e., HIGH+, HIGH-, LOW+, and LOW-; Morean et al., 2013, 2015) as dependent variables. Demographic, personality/affective (i.e., BDI/STAI/IRQ/NEO-derived neuroticism), and biomedical (i.e., menstrual phase for female participants, sleep quality) variables will be included as covariates should any be found to correlate significantly with magnitude of alcohol analgesia or relief ratings. A main effect of FH status such that FH+ individuals have greater magnitude of alcohol analgesia (i.e., greater increases in pain threshold/tolerance and decreases in pain intensity ratings), more positive/fewer negative subjective alcohol effects, and stronger expectancy of pain relief from alcohol consumption will be interpreted as evidence in support of H1 and H3. Lower ratings of alcohol-related relief from pain in FH+ individuals will provide support for H2.

To determine the independent contributions of expectancies and typical drinking behavior to alcohol analgesia, these measures will be included as independent variables in separate multiple regression analyses including interaction vectors with sex and FH, with magnitude of alcohol analgesia (e.g., increased pain threshold or reduction in pain intensity ratings) as the dependent variable. They will then be entered into simultaneous regression analysis to assess independence of their effects. A positive association between typical drinking and analgesic response to alcohol will provide support for H4. Risk of Type I error will be mitigated through the use of Tukey's HSD. Although not a primary aim, the relationship between individuals' rate of rise of BAC following alcohol consumption and magnitude of alcohol analgesia will be examined in exploratory analyses. For FH+ participants, potential effects of the sex of affected parents and concordance with the participants' sex (i.e., sex-matched vs. unmatched pairs) will also be assessed.

Aim 2. Imaging functional correlates of alcohol analgesia and its modulating factors.

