are disrupted in chronic pain, including default mode network (DMN), salience network (SN), executive control network (ECN), and subcortical limbic network (LN) (Martucci and Mackey, 2016). ICA will be conducted using the voxel-to- voxel processing stream in the CONN toolbox, which involves back-projection of ICs identified across subject and condition to identify spatial components, followed by back-projection of these components to individual subjects (Calhoun et al., 2001). ICs most closely matching networks of interest will be identified based on masks derived from NeuroSynth (Yarkoni et al., 2011). Second, seed-based fcMRI analyses will examine Fishers' r-to-z transformed correlations between the ICA-derived seed ROIs and all other voxels in the brain. Seed-based correlation analyses will be conducted in the Conn Toolbox (Whitfield-Gabrieli & Nieto-Castanon, 2012). Hybrid ICA-seed-based fcMRI has been shown to yield accurate and reproducible results (Franco et al., 2013; Kelly et al., 2010). We will examine interactions of group and condition on connectivity of these resting-state networks using repeated measures GLM, followed by simple main effects decomposition.

Task-based analyses: Alcohol-related changes in BOLD activity in pain- and reward-related brain structures during painful stimulation will be evaluated using a GLM-based approach in SPM12. Following convolution of the canonical hemodynamic response function with the heat stimulation paradigm at the single subject level, group-level effects of dose, sex, and FH on pain-related activations in ROIs and in whole brain will be assessed. To examine the changes in functional connectivity associated with alcohol analgesia, task-based data will be analyzed using the psychophysiological interaction (PPI) pipeline within the Conn Toolbox. PPI is a method of examining task-modulated increases in functional connectivity through GLM by yielding an interaction term (i.e., PPI regressor) from the product of a task's convolved time course (e.g., blocks of noxious thermal stimulation) and the time course from a seed ROI (O'Reilly et al., 2012). Relevant seed ROIs for this analysis will be generated using ICA as described above. We will examine task-dependent functional connectivity in pain- and reward-related networks, both between groups and within conditions, using rmGLM.

Aim 3. Test sex as a moderator of alcohol and FH effects.

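### The Aim 1 rule for H1 names the family-history main effect, but H1 is a family-history by dose interaction

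*Combined protocol and SAP*

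**What the plan says.** All places are in the combined protocol and SAP.

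- **Specific Aims, Aim 1 (H1):** "alcohol administration will be associated with greater reduction in pain sensitivity in FH+ than FH- individuals".
- **Data Analysis Strategy, Aim 1 (model):** "FH status will be included as an independent variable in repeated measures general linear models analyses (rmGLM; SPSS GLM procedure; repeated: dose". The dependent variables listed are the pain measures, relief ratings, expectancy and the subjective-effects (SEAS) scales.
- **Data Analysis Strategy, Aim 1 (decision rule for H1 and H3):** "A main effect of FH status such that FH+ individuals have greater magnitude of alcohol analgesia (i.e., greater increases in pain threshold/tolerance", with decreases in intensity ratings added. The same sentence also covers "more positive/fewer negative subjective alcohol effects" and expectancy of relief.
- **Power Analysis:** about 54% "power to detect interactive effects of FH and dose on these measures", the measures being pain intensity (d = .42) and threshold and tolerance (d below .26).
- **Data Analysis Strategy, Aim 2 (resting state):** "We will examine interactions of group and condition on connectivity of these resting-state networks using repeated measures GLM". The task-BOLD text lists effects of dose, sex and FH and does not settle which term is meant.
- **Data Analysis Strategy, Aim 3:** H7 is judged by a sex by dose interaction, and Empirical Question 1 by a sex by FH by dose interaction.
- **QST Procedure:** in each laboratory session QST is run before the beverage and again about 15 minutes after it.
- **Screening Procedure:** expectancy is collected at screening, before any dose.

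**The concern.** H1 is the first hypothesis of Aim 1 and the subject of the title. Its decision rule attaches a condition (a larger alcohol effect in FH+) to a model term that does not test that condition. SPSS reports the FH main effect and FH x dose as separate tests. An analyst who follows the named term and one who follows the parenthesis would report different p-values for H1. On raw scores the main effect can also respond to a stable FH difference in overall pain sensitivity that has nothing to do with alcohol.

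The SEAS measures share the sentence and the problem, as a secondary matter. Expectancy shares the sentence but not the problem: it has no dose level, so a plain FH comparison suits it. The rule for H2 names no model term and is outside this point.

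**Working it through.** **1. What each term tests.** Let ΔP and ΔA be the FH+ minus FH- mean difference under placebo and under alcohol.

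- FH main effect = (ΔP + ΔA)/2
- FH x dose = ΔA − ΔP

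H1 is a statement about ΔA − ΔP. If ΔP = ΔA ≠ 0, the main effect is non-zero although analgesia does not differ. If ΔA = −ΔP ≠ 0, analgesia differs and the main effect is zero.

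**2. Whether a change score rescues the rule.**

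- Alcohol-minus-placebo score: the FH effect on it equals FH x dose, but no repeated dose factor is then left, contrary to the stated model.
- Within-session pre-to-post change: QST is run before and after the beverage, so this score exists at both doses and dose can stay repeated. The FH main effect is then the average of the FH differences in the placebo change and the alcohol change. H1 still needs their difference, FH x dose.

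**3. The plan's own figure.** From the documents: 110 completers (Participants); d = .42 and d < .26 (Power Analysis); and "Power analyses were performed assuming two-tailed hypothesis tests. Effect sizes are reported as" Cohen's d, r or f². Not stated, so assumed: alpha .05, a 55:55 FH split and d in SD-of-difference units. Power is from the noncentral t with 108 df and noncentrality d·√(n1·n2/(n1+n2)); sex is left out of the model.

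- d = .42: .42 × √27.5 = 2.20, power 58.8%
- d = .26: .26 × √27.5 = 1.36, power 27.2%

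The stated figure of about 54% is not reproduced exactly at d = .42. A 37:73 split gives 54.1%, and so would d of about .40 at 55:55. Because split, alpha and units are unstated, this does not show the figure to be wrong, and nothing below rests on it.

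**4. Power of the two terms (illustration).** Further assumptions not in the documents: raw post-beverage scores, equal session SDs (set to 1), an FH effect δ under alcohol only, and session correlation ρ.

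- SD of difference = √(2(1−ρ)), so d for FH x dose = δ/√(2(1−ρ))
- SD of two-session mean = √((1+ρ)/2), so d for the main effect = (δ/2)/√((1+ρ)/2)
- Ratio, main effect to FH x dose = √((1−ρ)/(1+ρ))

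With d = .42 for FH x dose:

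| ρ | d, main effect | Power, main effect | Power, FH x dose |
|---|---|---|---|
| .5 | .242 | 24.3% | 58.8% |
| .6 | .210 | 19.4% | 58.8% |
| .7 | .176 | 15.0% | 58.8% |
| .8 | .140 | 11.3% | 58.8% |

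A simulation of 40,000 trials agrees: 58.9% and 24.5% at ρ = .5; 59.1% and 11.3% at ρ = .8.

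At d = .26 the figures are 27.2% for FH x dose and 12.2% to 7.4% for the main effect.

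If the pilot d is instead in session-SD units, then for ρ from .5 to .8:

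- d = .42: FH x dose 58.8% to 93.2%, main effect 24.3% to 21.0%
- d = .26: FH x dose 27.2% to 57.0%, main effect 12.2% to 11.0%

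**5. When the gap vanishes.** At ρ = 0 the ratio in step 4 is 1 and the two terms have equal power. That may happen with within-session change scores. If measurements have equal variance and every cross-session correlation equals r, the covariance of the two change scores is proportional to r − r − r + r = 0.

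**The case against.** The strongest reply is that the meaning is plain. The rule is not met by just any FH main effect: its qualifying clause requires larger increases or decreases in FH+. The plan powers FH by dose on these very outcomes, and the rules for sex use by-dose interactions. Elsewhere in Aim 1 the regressions are run "with magnitude of alcohol analgesia (e.g., increased pain threshold or reduction in pain intensity ratings) as the dependent variable", so the authors may have had a per-person change in mind, for which an FH effect would be right. This stands as evidence of intent, and it makes the point a wording correction. It does not make the named term the right one, because neither change-score reading works together with dose as the repeated factor.

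A reader might go further and infer that the plan would give false support to H1. The documents do not support that. It would need raw scores, an FH+ group that is less sensitive overall, and a qualifying clause that nobody checks. Within-session change scores would cancel a stable sensitivity difference. Ratings in the scanner are taken at individually calibrated temperatures, which limits the problem mainly to threshold and tolerance. No size for such a difference can be drawn from the documents.

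A reader might also take the drop from 59% to between 24% and 11% as a property of this trial. It is not: it depends on an outcome definition, an FH split and a session correlation that the documents do not give.

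**Conclusion.** The point holds as a mis-named term. Under the stated model the FH main effect averages over placebo and alcohol, and H1 is FH x dose. That follows from the model alone and needs no numerical assumption. The size of the consequence does need assumptions: about 59% power against 24% to 11% at d = .42 in SD-of-difference units, under the conditions in the working, narrowing to no gap when session scores are uncorrelated.

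It should not be inferred that the trial cannot test H1, since the planned model yields the right term. Nor should it be inferred that naming that term makes H1 well powered: for threshold and tolerance, power is about 27% at d = .26 in SD-of-difference units. The correction is worth making before analysis because it settles which p-value decides the leading hypothesis.

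**What to change.** In Data Analysis Strategy, Aim 1:

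- State that H1 is supported by an FH x dose interaction in which the alcohol-versus-placebo change (threshold and tolerance up, intensity down) is larger in FH+. An FH effect on the alcohol-minus-placebo difference is an equivalent statement.
- Use the same term for the SEAS measures.
- Test screening expectancy (the group-difference part of H3) by a plain FH comparison outside the dose-repeated model.
- Report any FH main effect on pain measures only as a difference averaged over doses.

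The cost is one or two sentences of analysis wording for H1 and SEAS, and a clause each for the other two. The planned model already produces FH x dose; sample size, procedures and data are unchanged.

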exclusionary, this maximum quantity will be considered in exploratory analyses given evidence it may modulate the acute effects of alcohol on cognitive performance (Lewis and [name], 2013). Expectancy of pain relief from alcohol intake will be measured using item 11 of the Alcohol Expectancy Questionnaire (Brown, et al., 1987) based on participants' responses to the item, "Alcohol can act as an anesthetic for me; that is, it can deaden the pain", expectancy will range from -10 (strong disbelief that alcohol relieves pain) to 10 (strong belief). We will also measure expectancy of pain relief from alcohol using the Expectancies for Alcohol Analgesia Inventory (Ditre et al., 2018) and a simple two item visual analog scale measure.

All participants will be provided with a pamphlet containing information about local mental health services; if desired, the PI or research assistant will facilitate contact with clinical services. Any subjects endorsing suicidal or homicidal intent during screening will be withdrawn from the study. [name], who is a licensed clinical psychologist, will then provide appropriate referral.

Participants who continue to qualify will be given a detailed description of the two laboratory sessions, the tasks and measures to be collected, and reasons for urine samples (drug and pregnancy testing). Baseline quantitative sensory testing (QST) measures of pain sensitivity and tolerance will be taken after participants' eligibility is confirmed and they indicate their willingness to continue. Participants will provide their own transportation to screening sessions. Participants will be paid \$15 for completing the screening phase of the study, which will require approximately 1-2 hours.

Screening Measure	Domain	Exclusionary Cutoff
BDI-II	Depressive Symptomology	≥ 20 (moderate depression)
STAI	State/Trait Anxiety	Not Exclusionary
AEQ	Alcohol Expectancies	Not Exclusionary
AUQ	Alcohol Use Pattern	Not Exclusionary
AUDIT	Alcohol Use Disorder Sx	≥ 8
PILL	Somatic preoccupation /neuroticism	Not Exclusionary
FTQ	FH Assessment	Not Exclusionary
PSQI	Sleep Quality	Not Exclusionary
BRS	Resilience to stressors	Not Exclusionary
DIS	Ability to tolerate physical discomfort	Not Exclusionary
EAA	Expectancies regarding pain relief from alcohol	Not Exclusionary
PCS	Pain catastrophizing	Not Exclusionary
PASS-20	Pain-related Anxiety	Not Exclusionary
IRI	Empathy	Not Exclusionary

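### The support rule for H3 does not use the planned expectancy–analgesia regression, so H3 can be declared supported even if expectancy does not predict analgesia

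*Combined protocol and SAP*

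**What the plan says.** All references are to the combined protocol and SAP.

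- **Section 5, Specific Aims, Aim 1** states H3: "FH+ individuals will have stronger positive expectancies regarding alcohol analgesia, which will predict analgesic response to alcohol administration". H1, on reduction in pain sensitivity, is a separate hypothesis.
- **Section 6, Data Analysis Strategy, Aim 1, first paragraph** gives one support sentence for H1 and H3 together. It opens "A main effect of FH status such that FH+ individuals have greater magnitude of alcohol analgesia", continues with "more positive/fewer negative subjective alcohol effects", and closes with "stronger expectancy of pain relief from alcohol consumption will be interpreted as evidence in support of H1 and H3". Every item is a difference between FH groups. Expectancy is listed as a dependent variable in the models repeated on dose.
- **Same section, second paragraph** plans separate and then simultaneous regressions on magnitude of analgesia, "To determine the independent contributions of expectancies and typical drinking behavior to alcohol analgesia", with sex and FH interaction vectors. The only support rule that follows is "A positive association between typical drinking and analgesic response to alcohol will provide support for H4".
- **Section 6, Screening Procedure**: "Expectancy of pain relief from alcohol intake will be measured using item 11 of the Alcohol Expectancy Questionnaire". Two further measures are named, the Expectancies for Alcohol Analgesia Inventory and a two-item VAS. Laboratory Sessions repeats the BDI-II and STAI and adds the IRQ, but mentions no repeat of expectancy.
- **Section 6, Power Analysis** gives pilot d = 1.12 for FH on expectancy, d = 0.42 for FH on alcohol-related reduction in pain intensity and below 0.26 for threshold and tolerance, and about 54% power for the FH-by-dose effects. Correlations with reduced pain sensitivity lie between 0.26 and 0.44, with about 80–99% power.

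**The concern.** The clause "which will predict analgesic response to alcohol administration" is what makes H3 a hypothesis about mechanism; without it, H3 only describes two groups. The Summary of section 4 names expectancies as a modifiable target for treatment, and that inference needs the predictive part to be true. The plan collects the data and fits the model that would show it, but no result of that model bears on the H3 verdict. A report that followed the stated rule could announce support for H3 beside a flat or reversed expectancy slope.

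The sentence also merges H1 and H3, and counts subjective effects (SEAS) towards both although neither hypothesis is stated in those terms.

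**Working it through.** **Inputs.** 110 completers (Participants); two-tailed tests and the pilot effects above (Power Analysis). Two inputs are assumptions: alpha 0.05, which is not stated for the behavioural tests, and FH groups of 55/55, because the plan equalises only sex.

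**1. Reproducing the plan's power.** For two groups, ncp = d·√(n₁n₂/(n₁+n₂)), compared with t(0.975; 108) = 1.982. With 55/55 the root is √27.5 = 5.244.
- d = 0.54: ncp 2.83, power 0.80. d = 1.12: ncp 5.87, power > 0.999. Both fit the stated figure of over 80%.
- Correlations, Fisher z, N = 110: atanh(0.26)·√107 = 2.75, power 0.79; atanh(0.44)·√107 = 4.88, power 0.998. Both fit the stated 80–99%.

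**2. Item-by-item reading** (the expectancy item alone supports H3). Suppose expectancy is unrelated to analgesia. The chance of declaring H3 supported is then simply the power for the FH difference in expectancy:

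| True d, FH on expectancy | FH split | P(H3 declared) |
|---|---|---|
| 1.12 | 55/55 | > 0.999 |
| 1.12 | 22/88 | 0.996 |
| 0.8 | 55/55 | 0.986 |
| 0.5 | 55/55 | 0.74 |
| 0.3 | 55/55 | 0.34 |

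**3. Joint reading** (all listed items must hold). The probability cannot exceed that of the least likely item. With 55/55, the FH difference in analgesia is significant with probability 0.59 at d = 0.42, 0.27 at d = 0.26, and 0.025 in the hypothesised direction at d = 0. These are upper limits, because the subjective-effects item is also required. (The plan's own figure for the FH-by-dose effects is about 54%; d = 0.42 gives that at roughly 37/73. Nothing here depends on the difference.)

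**4. Rule requiring both parts of H3.** With d = 1.12 and a zero slope: > 0.999 × 0.025 ≈ 0.025. With both parts true: about 0.79 at r = 0.26 and 0.998 at r = 0.44.

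**5. Does FH need to be in the regression?** Simulation with FH on expectancy d = 1.12, FH on analgesia d = 0.42, and no slope within FH groups: a significantly positive expectancy coefficient appears in about 18% of runs without FH in the model, and in 2.3–2.7% with it.

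**6. Power after adjusting for FH.** If the pilot correlations are marginal, convert d to r by d/√(d²+4): FH with expectancy 1.12/√5.254 = 0.489; FH with analgesia at d = 0.42, 0.42/√4.176 = 0.206. At r = 0.26 the partial correlation is (0.26 − 0.489 × 0.206)/√((1 − 0.239)(1 − 0.042)) = 0.187. Power is Φ(atanh(0.187)·√106 − 1.96) ≈ 0.49. The same steps give about 0.66 at FH–analgesia d = 0.26 and about 0.89 at d = 0. At r = 0.44 power stays at 0.99 or above in all three cases.

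**The case against.** The strongest reply is that the test is not missing. The regression of analgesia on expectancy is planned and powered, and its result will be available whatever the rule says. That stands. A reader might infer that the plan never tests whether expectancy predicts analgesia; the documents do not support this. What is missing is the link from that result to H3.

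A reader might also infer that an FH difference in expectancy alone is enough, so that H3 will almost surely be declared supported. That is one reading of an ambiguous sentence. Its list is joined by *and*, so it can equally require greater analgesia and the subjective effects as well. Even item by item, near-certainty needs a true effect close to the pilot d = 1.12. The wording is also evidence in support, which is softer than a formal declaration.

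The joint reading does not rescue the rule. It still contains no expectancy–analgesia association, and it makes a true H3 depend on an FH-by-dose effect for which the plan states only about 54% power.

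Two smaller replies have some force. Aim 1 introduces H1 from differences in subjective response, so SEAS has a rationale there; reporting it as secondary is partly a matter of judgement. Listing expectancy in a dose-repeated model may be loose wording, since the criterion is a main effect of FH, which for a variable measured once is the between-subject comparison.

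**Conclusion.** The concern holds as a mismatch between hypothesis and decision rule: on either reading, H3 can be called supported with a zero or negative expectancy slope. The chance of this when the second part is false is above 99% on the item-by-item reading at d = 1.12, falling to 74% at d = 0.5 and 34% at d = 0.3. On the joint reading it is at most about 59% (FH–analgesia d = 0.42), 27% (d = 0.26) or 2.5% (no FH effect on analgesia). All figures assume alpha 0.05 and, except the 22/88 row, equal FH groups. The mismatch itself depends on none of these numbers; only its size does. It should be corrected before analysis.

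**What to change.** Give H1 and H3 separate rules.

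- **H1:** judge on FH differences in alcohol-related change in pain threshold, tolerance and intensity. Report SEAS as secondary.
- **H3:** declare supported only if both hold: (a) expectancy is higher in FH+ in a between-subject FH × sex comparison, since expectancy is described only at screening and has no dose-specific values; and (b) the expectancy coefficient is significantly positive in the regression already planned, on alcohol-minus-placebo change. Include FH and sex as main effects and centre the interaction coding, so that the coefficient has a clear meaning.
- Name in advance one of the three expectancy measures and one analgesia outcome. The 2.5% limit does not hold if any of several outcomes may count.

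This changes wording only; no new data are needed. The cost is that H3 becomes harder to support. Power is about 79% at r = 0.26 if that correlation holds within FH groups. If it is marginal, power could be as low as about 49% when FH also affects analgesia at d = 0.42. It stays at about 99% at r = 0.44.
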